3.1.3 Definition of Baseline

Baseline is defined as the last measurement prior to the first treatment dose of study drug.

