10.3 SCHEDULE OF ASSESSMENTS FOR SUBJECTS AGED 2 YEARS-17 YEARS

	SCREENING	TREATMENT					FOLLOW-UP
Duration	Up to 21 days	12 WEEKS (equivalent of 84 days)					10-14 days
Day		1	7-10	28	56	84	94-98
Visit ¹¹	1	2	3 ³	4	5	6	7 ^{9,10}
Informed Consent	х						
Eligibility ^{1,8}	х	х					
Demographics	х						
Medical History	х						
Physical Examination	х					х	
Vital Signs ²	х	х	Х	X	х	х	
Urine Pregnancy Test ⁴	х	х	х	х	х	х	
Clinical Laboratory tests ⁵	х					х	
Haematology ⁶	х			X		х	
Iron markers ⁶	х			Х		Х	
PK assessment PK Blood Sampling for maltol/maltol glucuronide and iron markers ⁷		х	х				
Randomisation ⁸		х					
Dispense Study Drug		х	х	х	х		
Return Study Drug for Accountability			х	х	х	х	
Palatability questionnaire		х		х			
Adverse Events		х	х	х	х	х	х
Concomitant Medications and Procedures	х	х	х	х	х	x	х
Compliance reminder		х	х	Х	х	х	
Compliance assessment			х	Х	х	Х	

CONFIDENTIAL Page 56 of 80

- 1. A subject may be retested once for laboratory criteria that do not meet protocol criteria so long as randomisation occurs no more than 21 days from the initial screening visit date (if eligible).
- 2. Vital Signs body weight, height, systolic/diastolic blood pressure, pulse, and body temperature at each visit. Patient weight should be recorded at each clinic visit and drug dosing administered as per last clinic visit weight.
- 3. Visit 3 (PK Day 2) only applicable for the first 12 subjects randomised to ferric maltol group in each age group (2 yrs -9 yrs, 10 yrs-17 yrs).
- 4. Urine pregnancy test for female subjects of childbearing potential only.
- 5. Clinical Laboratory tests including:
 - a. Clinical Chemistry: Vitamin B12, folate, ALT, AST, alkaline phosphatase, gamma-glutamyl transpeptidase (GGT), total bilirubin, creatinine, amylase, blood urea nitrogen (BUN), phosphorous, sodium, potassium, chloride, calcium, total cholesterol, uric acid, glucose, total protein, albumin
- 6. Haematology and Iron markers:
 - a. Haematology: Red blood cell count, haemaglobin, haematocrit, mean cell volume (MCV), white blood cell count (total and differential (% and absolute), absolute reticulocyte count and platelet count.
 - b. Iron Markers: serum iron, transferrin, transferrin saturation (TSAT), total and unsaturated iron binding capacity (TIBC, UIBC) and ferritin.

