- 7. On PK study Day 1 (Visit 2) and PK study Day 2 (Visit 3) for the first 12 subjects in each age group (2 yrs 9 yrs, 10 yrs-17 yrs, respectively) who have been randomised to ferric maltol groups have baseline PK blood samples collected immediately prior to ferric maltol dosing (0 hr). Subjects will then have further PK blood samples collected at two (2) additional times between 0.5 hr and 6 hrs after dosing on Visit 2 and 3; the post-dose PK sample time collection windows will be 0.5-1h, 1.0-2.0 hrs, 2.0-3.0 hrs, 3.0-4.0 hrs and 4.0-6.0 hrs. For each individual subject, the post-dose PK blood sampling schedule will be the same on PK Day 1 and PK Day 2. Post-dose blood samples should be collected within the time windows allocated only. N.B: samples should be taken at least 1.0 hr apart.
 - In the event of an administered dose not being consumed or partially consumed by the patient this will be noted as a missed dose and will not be repeated.
- 8. Eligibility laboratory sampling/assessments must be completed before the subject is randomised and before the first dose of study treatment taken. A minimum number of 18 subjects must be recruited into each age group (2 yrs -9 yrs, 10 yrs-17 yrs) and a minimum of 25% of either sex must be recruited and at least 49 subjects per arm.
- 9. Subjects who have at least one dose of study medication and withdraw earlier from the study undergo Visit 7 (Day 94-98) assessments (excluding those who have withdrawn consent).
- 10. Visit 7 is conducted by telephone, unless the Subject has an ongoing AE that requires physical examination or investigations for assessment/management. Visit 7 will take place 10-14 days after Visit 6 (Week 12) unless subject discontinued treatment early. All withdrawn subjects should undergo Visit 7 within 10-14 days after the last dose of study drug (if the subject agrees in the case of withdrawn consent).
- 11. Visit Windows: Maximum of 21 days between screening and randomisation. The Subject must visit to complete:
- a. Visit 2 and Visit 3: must be 6-9 days between the scheduled PK days.
- b. Visit 4: +/- 5 days relative to date of Visit 2/first dose administered
- c. Visits 5 to 6: +/- 5 days relative to date of Visit 2/first dose administered
- d. Visit 7: 10-14 days after Visit 6 (unless subject discontinued treatment early see Note 10

CONFIDENTIAL Page 57 of 80

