10.8.2 Pharmacokinetics

Blood samples for maltol and maltol glucuronide on each PK day

Blood samples will be collected at the required times on the PK assessment days relative to the time of ferric maltol morning dosing: pre-dose then two further times between 0.5-10 hours post-dose in the 2-17 years age group and pre-dose then three further times between 1-12 hours post-dose in the 1 m to less than 2 years age group (see Section 10.3 and section 10.4).

Following collection and mixing, blood samples will be centrifuged, and the resultant plasma samples separated and stored at -20°C at the study site, prior to collection and onward shipping to the central laboratory on dry ice for subsequent assay of maltol and maltol glucuronide plasma concentrations using appropriately validated bioanalytical methods. Full

CONFIDENTIAL Page 61 of 80

details of the required sample collection, processing and handling logistics will be specified in the study specific Laboratory Manual. Samples will be destroyed at the end of the study, once all analyses are complete.

Blood samples for iron markers on each PK day

Blood samples will be collected at the required times on the PK assessment days, relative to the time of ferric maltol dosing: pre-dose then two further times between 0.5-6 hours post-dose in the 2-17 yrs age group. Same times as blood samples for maltol/maltol glucuronide for each individual (see Section 10.3 and section 10.4.).

Following collection and mixing, blood samples will be centrifuged, and the resultant serum samples separated and split into 2 aliquots at each timepoint. Ambient serum samples will be shipped to the central laboratory for subsequent assay of serum iron, transferrin, transferrin saturation (TSAT), total and unsaturated iron binding capacity (TIBC, UIBC. Frozen serum aliquot will be stored at site (-20°C) for later onward shipping on dry ice to the central laboratory. Full details of the required sample collection, processing and handling logistics will be specified in the study specific Laboratory Manual. Samples will be destroyed at the end of the study, once all analyses are complete.

PK blood sample scheduling in the 2-17 yrs age groups:

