 - Subjects randomised to ferrous sulfate oral liquid will not need to complete the PK period, they will remain on oral ferrous sulfate liquid until Week 12.
 - Ferrous sulfate 125 mg/ml (25 mg elemental iron) or equivalent dose will be used for all children/adolescents. To maximise the iron replenishment for subjects within this group as well; aged 2 17 yrs will be dosed 0.24ml (6mg elemental iron) per kg body weight per day, up to a maximum of 8ml given daily in two divided doses.
- Assigned treatment phase: 12 weeks open label treatment for ferric maltol children aged
 1 month to less than 2 years.

- Once the PK samples collected from the pre-assignment phase have been analysed for subjects aged 1 month to less than 2 years, and following data review it has been confirmed that they can enroll in the treatment phase, they will be assigned to receive ferric maltol oral suspension and start the 0.1 ml/kg/dose, BID (Maximum 2.5ml BID) dose on Visit 2 and continue for 7-10 days. On Visit 3 (PK Day 2), following baseline pre-dose blood sample and urine sample, subjects will take a single dose of 0.1 ml/kg ferric maltol suspension under supervision. Further three PK blood and urine samples will be collected up to 12 hours post dose. Subjects will continue until week 12.
- End of study: Week 12 visit.
- Post-treatment safety follow-up: 10-14 days following study completion of the treatment period or premature discontinuation.

Table 2.1: Schedule of Assessments for subjects aged 2 years-17 years.

	SCREENING		TREATMENT				FOLLOW- UP
Duration	Up to 21 days	(e	12 quivale	: WEE		ays)	10-14 days
Day		1	7- 10	28	56	84	94-98
Visit 11	1	2	3 8	4	5	6	7 ^{9,10}
Informed Consent	х						
Eligibility ^{1,8}	х	х	х				
Demographics	Х						
Medical History	х						
Physical Examination	х					х	
Vital Signs ²	х	х	х	х	х	х	
Urine Pregnancy Test 4	х	х	х	Х	х	х	
Clinical Laboratory tests ⁵	х					х	
Haematology ⁶	х			Х		х	
Iron markers ⁶	х			Х		х	
PK assessment PK Blood Sampling for maltol/maltol glucuronide and iron markers ⁷		Х	х				
Randomisation ⁸		х					
Dispense Study Drug		х	Х	Х	Х		
Return Study Drug for Accountability			х	х	х	х	

	SCREENING	TREATMENT			FOLLOW- UP			
Duration	Up to 21 days	12 WEEKS (equivalent of 84 days)						
Day		1	1 7- 28 56 84		94-98			
Visit 11	1	2	3	4	5	6	7 ^{9,10}	
Palatability questionnaire		х		х				
Adverse Events		х	х	х	х	х	х	
Concomitant Medications and Procedures	х	х	х	х	х	Х	х	
Compliance reminder		х	х	х	х	х		

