2.2.2 Randomisation

Approximately 110 male and female children from 1 month to 17 years of age, with iron deficiency anaemia at approximately 20 sites will be recruited. The number of subjects will be reduced if the study is stopped following a successful interim analysis.

Subjects aged 2 to 17 years will be 1:1 randomised to ferric maltol and ferrous sulfate, with 49 subjects in each arm. Subjects then will be further divided into 2 age groups: 2 yrs – 9 yrs and 10 yrs -17 yrs. A minimum of 18 subjects must be recruited into the 2 yrs - 9 yrs and 10 yrs – 17 yrs age groups across the study as a whole and a minimum of 25% of either sex must be recruited.

A maximum of 12 subjects will be recruited in the 1 month to less than 2 years age group.

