2.2.4 Sample Size Determination

In total up to 110 patients will be recruited into the study. Up to 98 subjects will be randomised in the 2 -17 years cohort and up to 12 subjects will be assigned in the <2 years cohort.

The aim is to recruit up to 49 subjects in each treatment group in the 2 – 17 years cohort. At least 12 subjects in each age group respectively (i.e. 24 subjects in total) will be included in the PK analysis group in the ferric maltol oral suspension group. A sample size of 49 in the Ferric Maltol group provides at least 80% power to demonstrate that the lower bound of the 95% confidence interval for increase in Hb at 12 weeks, compared with baseline, is above zero. This assumed that the standard deviation (SD) of the change from baseline is 1.2 g/dL or lower and the true mean change is at least 0.5 g/dL.

Every effort will be made to recruit up to 12 subjects in the under 2's age group but in case of reasons of feasibility it cannot be completed, then the study may be completed without that cohort.

If less than 91 subjects in total have been randomised when 32 ferric maltol subjects have completed treatment (or withdrawn from the study), then an interim analysis of the primary effectiveness endpoint (change in Hb concentration from baseline to Week 12) will be conducted. If significant, the study will stop recruitment. If not significant, the study will continue (all subjects will be assigned to ferric maltol) until 54 subjects have been recruited in the ferric maltol arm.

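### Read literally, the SAP baseline rule gives the planned 24 of 49 ferric maltol children aged 2–17 a Day 1 baseline for five iron markers, and every ferrous sulfate child a screening baseline

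*SAP*

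**What the plan says.** The general baseline rule in SAP 3.1.3 reads: "Baseline is defined as the last measurement prior to the first treatment dose of study drug". It makes no distinction by visit, by routine or PK sample, or by arm.

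In the schedule for ages 2–17 (Protocol 10.3, SAP Table 2.1), routine iron markers are drawn at Screening, Day 28 and Day 84. A separate row, "PK Blood Sampling for maltol/maltol glucuronide and iron markers", is marked at Visits 2 and 3. Its footnote applies to the first 12 children in each of the two age groups "who have been randomised to ferric maltol groups have baseline PK blood samples collected immediately prior to ferric maltol dosing (0 hr". Protocol 10.8.2 sends the serum to the central laboratory for "subsequent assay of serum iron, transferrin, transferrin saturation (TSAT), total and unsaturated iron binding capacity (TIBC, UIBC". Ferritin and Hb are not on that assay list.

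The comparator arm has no such sample: "Subjects randomised to ferrous sulfate oral liquid will not need to complete the PK period" (SAP 2.2.1). First dosing is on the day of randomisation (Protocol 9.2), and randomisation may be up to 21 days after Screening.

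SAP 3.4.2 reports change in iron markers from baseline to Weeks 4 and 12 for each treatment group, split by age group. SAP 3.1.5 makes the secondary endpoints descriptive only.

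**The concern.** A last-value-before-dose rule is harmless when both arms have the same pre-dose samples. Here they do not. Whether a child has a Visit 2 iron result depends on the assigned arm, so the rule ties the baseline source to treatment. Randomisation cannot balance that.

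The two samples are not interchangeable. The screening sample is used to decide eligibility, including TSAT below 20% for children who qualify on the wider ferritin limit. The Visit 2 sample has no such role, may be taken up to 21 days later, and is drawn immediately before a supervised dose. Single-agent oral iron need stop only 7 days before Screening, so values could also drift downwards between the two samples.

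Any mean shift between them enters the change scores of part of one arm and of nobody in the other. The ferric maltol mean change, which serves the iron-marker objective, would itself blend two definitions of baseline.

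**Working it through.** **Count of PK children.** SAP 2.2.4: "At least 12 subjects in each age group respectively (i.e. 24 subjects in total) will be included in the PK analysis group". This reproduces as 12 × 2 age groups = 24. Protocol 12.1 gives 36, which is consistent with adding the 12 infants (24 + 12) and does not alter the count at ages 2–17.

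**Arm size.** SAP 2.2.2: "Subjects aged 2 to 17 years will be 1:1 randomised to ferric maltol and ferrous sulfate, with 49 subjects in each arm".

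**Baseline source under the literal rule, ages 2–17, for serum iron, transferrin, TSAT, TIBC and UIBC**

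| Group | Visit 2 pre-dose | Screening or retest |
|---|---|---|
| Ferric maltol (49) | 24 (24/49 = 49.0%) | 25 |
| Ferrous sulfate (49) | 0 | 49 |

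**Effect on the mean change.** Let s be the mean of Visit 2 minus Screening among the PK children. Their change from Visit 2 equals their change from Screening minus s. Relative to a screening baseline for everyone, the ferric maltol mean change moves by −(24/49) × s, and the ferrous sulfate mean by 0.

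The documents give no value for s. Assumed values, in the units of the marker:

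| s (assumed) | Artefact in the ferric maltol mean change |
|---|---|
| −2 | +0.98 |
| −1 | +0.49 |
| 0 | 0 |
| +1 | −0.49 |
| +2 | −0.98 |

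**How the share varies**
- If the ferric maltol arm grows to 54 after an unsuccessful interim analysis: 24/54 = 44%, taking all 54 as aged 2–17.
- If recruitment stops at the interim analysis: 24/32 = 75%. This assumes that all 32 are aged 2–17, that all 24 PK children are among them, and that no further ferric maltol children of that age are enrolled.
- By age group, the share is 12 divided by the number of ferric maltol children in the group, or 100% when there are 12 or fewer. An age group at the permitted minimum of 18 would have about 9 per arm at 1:1. All 9 ferric maltol children would then be PK children, against none on ferrous sulfate. Fewer than 24 would be sampled overall in that case.

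**Markers outside the problem.** At ages 2–17 Hb and ferritin have no listed Visit 2 assay, so their baseline is the screening or retest value in both arms.

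**The case against.** The strongest reply is that the SAP never says PK-day results enter the iron-marker dataset. The schedule has separate rows for the two kinds of sample, PK data have their own population and section, and the programming specifications are in another document. This stands as far as intent is concerned. It does not settle the text. Nothing in SAP 3.1.3 excludes PK samples, the schedule footnote calls the 0 h draw a baseline sample, and SAP 3.4.2 lists corrected serum iron, otherwise a PK analyte, among the Week 4 and 12 markers. A programmer following the rule as written would take the Visit 2 value.

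The second reply is that little depends on the comparison. The iron-marker objective names ferric maltol only, and no between-arm test or estimate is planned. That stands, and it limits the harm to side-by-side descriptive tables and to a blended ferric maltol mean.

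Third, regression to the mean is a weak argument for these markers. Eligibility rests on Hb and ferritin. TSAT enters only through the alternative criterion, and the other four markers not at all. That stands too.

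Fourth, a Day 1 value is closer to treatment and was not used for selection, so for a within-arm change it has merit. This is a fair cost to set against the fix.

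A reader might infer that the rule works against ferric maltol. That would follow only if the marker rises between Screening and Day 1, which the documents do not show. A reader might also take 75% as the expected share after early stopping. The interim trigger counts children who have finished, and others would normally still be on treatment and enlarge the denominator, so 75% is close to an upper bound.

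**Conclusion.** The point holds as a defect in how the rule is written. Followed literally, it makes the baseline source depend on the arm for serum iron, transferrin, TSAT, TIBC and UIBC at ages 2–17: 24/49 (49%) against 0/49. That count needs no assumption beyond the planned numbers and the literal reading.

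The resulting artefact is about 0.49 times the mean Screening-to-Day-1 shift. Its size and sign cannot be derived from the documents, and it may be zero. The share differs by age group and with early stopping.

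The consequence is confined to secondary, descriptive tables. A reader might infer that the primary Hb result is compromised, or that a formal treatment comparison is biased. Neither follows: Hb baselines at these ages come from Screening or its retest in both arms, and no test of iron markers between arms is planned.

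**What to change.** Add to SAP 3.1.3 that, for the iron-marker change endpoints at ages 2–17, baseline is the last routine pre-randomisation sample (Screening or its permitted retest) in both arms, and that Visit 2 pre-dose PK samples are used only for the PK analyses. Infants keep their Visit 2 baseline; they are single-arm and already reported in their own age group.

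The Day 1 share then becomes 0/49 in each arm and the artefact from baseline source is zero. The cost is the added SAP text and one derivation flag, before database lock, with no new data and no subjects lost. The small downside is that the PK children's baseline becomes older than their Day 1 value. A supplementary summary within ferric maltol, using the Day 1 value for those children, covers it. If the sponsor already intends to keep PK samples out of this baseline, the same text records that.

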3.1.4 Summary Statistics

Categorical data will generally be summarised with counts and percentages of subjects. The denominator used for the percentage calculation will be clearly defined. Continuous data will

generally be summarised with descriptive statistics including n (number of non-missing values), mean, median, standard deviation, range (minimum and maximum).

For PK parameters, descriptive statistics will also include coefficient of variation (CV %), geometric mean (GM) and GM CV (%).

3.1.5 Hypothesis Testing

Hypothesis testing will be performed for the interim analysis to test the hypothesis that the ferric maltol Hb change from baseline to Week 12 is > 0. If an interim analysis is conducted, a Pocock spending function will be used; the interim analysis will be based on a (100-3.45)% two sided confidence interval.

The efficacy primary endpoint will also involve hypothesis testing. If no interim analysis is conducted the hypothesis testing will be based on a 95% two-sided confidence interval. If the study does not stop after the interim analysis, the final analysis will be based on a (100-2.57)% two sided confidence interval.

The study safety primary endpoints will be analysed by descriptive statistics only. The secondary endpoints will be analysed by descriptive statistics only. Thus, no formal testing strategy or adjustments of the Type I error will be employed for the evaluation of secondary endpoints.

3.1.6 Handling of Dropouts and Missing Data

In general, missing data will not be imputed unless otherwise specified. Only observed data will be used in the summaries and analyses.

For adverse events (AEs) with incomplete or missing dates, imputation for start and stop dates relative to the start date of study drug is necessary to define an AE as treatment emergent. For missing AE start day, the 1st of the month will be used. If this day is before the day of study drug start and the end date of AE is on or after the date of first study drug, or if the AE end date is completely missing, the start date of study drug will be used. For missing start day and month, the start day and month will be January 1st. If January 1st is before start day and month of study drug, the start date of study drug will be used.

Partial dates for concomitant medications will be imputed to determine prior and concomitant status. Partial dates will be imputed as above for AEs. If the start date is completely missing, the start date will equal the date of first study drug. If the stop date is known and prior to the first date of study drug, the start date will equal the stop date of concomitant medication. If the stop date is completely missing, the concomitant medication will be considered as ongoing.

3.2 Analysis Populations

3.2.1 Randomised Population/Intention to treat (ITT) Population

The ITT Population is defined as all subjects who were randomised/assigned to treatment arms.

3.2.1 Modified Intention to treat (mITT) Population

The mITT Population is defined as all subjects in the ITT population who have received at least 1 treatment dose.

3.2.2 Per-Protocol (PP) Population

The PP Population will consist of those randomised/assigned subjects who do not have major protocol deviations during the study. Data will be reviewed during a data review meeting prior to database lock to identify subjects to be included/excluded from the per-protocol population. The subjects to be included/excluded will be noted in a note to file (NTF).

3.2.3 Safety Population

The Safety Population is defined as all randomised/assigned subjects who receive at least one dose of study drug. All safety data will be analyzed using the Safety Population.

